### 1.1.8 ENHANCED MONITORING PLAN

An enhanced monitoring plan will be used in this study to address the risk of a potential delay in treatment of vulvar HSIL. The feasibility of this approach was demonstrated in the Phase 2b study of cervical HSIL. Given that vulvar disease progresses slowly to vulvar cancer if untreated, the proposed enhanced monitoring plan is expected to maintain the safety of subjects in this study. First, only Gynecology-Oncologists and Gynecologists who are well experienced in the monitoring and management of vulvar disease will be used as study Investigators. Inclusion into the study will require histologic confirmation of the diagnosis of the vulvar disease as vulvar HSIL, and not carcinoma, by two independent expert pathologists from the PAC (see Section 10.4.2). Women with differentiated VIN, which is more likely to progress faster and is not typically HPV-related is specifically excluded from study entry. By contrast, HPV-associated vulvar HSIL does not progress rapidly, typically taking years to manifest and progress, making enhanced monitoring feasible [24].

Throughout the study, there will be frequent vulvoscopy as well as photographic documentation and analysis of the lesion size (see Section 6.1). Colposcopy will also be performed at Day 0 and during the study given that concurrent disease in the lower genital tract can occur. A Data Safety Monitoring Board will be utilized to review subject safety data and advise on any study-level safety concerns. Investigators always have the option of performing ad hoc vulvar biopsies to rule out suspected disease progression. Additional treatment (e.g., additional excision, ablation, or medical therapy) may be carried out, if deemed necessary according to Investigator judgment.

### 1.1.9 VGX-3100

VGX-3100 encodes HPV-16 E6/E7 and HPV-18 E6/E7 antigens. The plasmids were designed and constructed using proprietary synthetic vaccine (SynCon™) technology. This process involves synthetically deriving consensus genes across multiple strains and optimizing DNA inserts at the genetic level to allow high expression in human cells. Together, VGX-3100 and the CELLECTRA™ device represent an integrated investigational product designed as a non-surgical treatment of HPV-16/18-related cervical HSIL (CIN2, CIN3) via an immune response directed against HPV-16/18. Further information about VGX-3100 is provided in the Investigator's Brochure.

### 1.1.10 ELECTROPORATION

VGX-3100 is delivered using the CELLECTRA™ *in vivo* electroporation (EP) device. EP is a physical method of tissue transfection whereby the generation of short, controlled electrical pulses creates a localized electric field at the injection site of the DNA vaccine which increases cell membrane permeability and improves the transfection of DNA and subsequent immunogenicity [25, 26]. Electroporation increases the uptake of plasmid DNA, thereby enabling increased expression and enhanced vaccine immunogenicity by 10 to 100 fold [27, 28]. This technology has been used for more than three decades by molecular biologists for cell transfection and has demonstrated versatility in use, as shown by its functionality in combination with a range of molecules, tissue types, disease indications, and across species [29].

This study will use the CELLECTRA™ 2000 device which has been used in 26 trials with 3795 doses administered to human subjects as of September 30, 2016 with no significant safety issues identified. Further information about the CELLECTRA™ 2000 device can be found in the Investigator's Brochure and device User Manual.

### 1.1.11 IMIQUIMOD CREAM, 5%

Imiquimod Cream, 5% is a licensed product intended to be used in this study concomitantly with the investigational product and device. Imiquimod Cream, 5% will be centrally sourced, supplied in single-use packets (24 per box), each of which contains 250 mg of the cream, equivalent to 12.5 mg of imiquimod. The product manufacturer is Perrigo, Yeruham 80500, Israel.

### 1.1.12 STUDY RATIONALE

This pilot study is being conducted in a population with vulvar dysplasia using a randomized, open-label design to demonstrate the efficacy of VGX-3100 followed by EP in women with vulvar HSIL associated with HPV-16/18 either alone or in combination imiquimod. The overall aim is to determine if treatment with VGX-3100 could allow women with vulvar HSIL to avoid or minimize surgical treatment procedures. Proof of concept that VGX-3100 can induce resolution of both HPV-associated dysplastic lesions and the underlying HPV-16/18 infection was shown in a Phase 2b study of cervical intraepithelial neoplasia (CIN). The similar underlying pathogenic mechanisms between cervical and vulvar HSIL form the basis of the clinical hypothesis that VGX-3100 could be a non-surgical therapeutic option for the treatment of vulvar HSIL, which is a significantly under met medical condition. A VGX-3100 with imiquimod-administration study drug is also included, given the prevalent use of imiquimod as a topical medical treatment of vulvar lesions, to investigate if a more robust immune response is achieved with VGX-3100, to potentially increase regression of vulvar HSIL.

### 1.1.13 DOSE AND REGIMEN RATIONALE FOR VGX-3100

A total dose of 6 mg VGX-3100 DNA has been selected for this study based on previous human experience with VGX-3100, preclinical data with VGX-3100 and other DNA vaccines, and the safety and immunogenicity data generated in the HPV-001, HPV-003, and HPV-101 studies. In HPV-001 trial, the 6 mg dose was delivered IM followed by EP, which showed trends toward higher response rates and magnitudes of IFN- $\gamma$  ELISpot

responses compared to the low (0.6 mg) and mid-dose (2 mg) cohorts without significant safety issues [30].

#### **1.1.14 RATIONALE FOR IMIQUIMOD**

Imiquimod cream is prescribed for the topical treatment of certain skin growths including external genital and perianal warts. Therefore, imiquimod may be able to be used synergistically with VGX-3100.

Randomized controlled trials have shown that the application of topical imiquimod 5% is effective for the treatment of vulvar HSIL although it is not approved by the US Food and Drug Administration for this purpose. Imiquimod is currently recommended as a non-surgical, off-label treatment option for vulvar dysplasia by the American College of Obstetricians and Gynecologists (ACOG). Published regimens include three times weekly application to affected areas for 12 – 20 weeks, with colposcopic assessment at 4-6 week intervals during treatment [17].

This study will include a study group to explore whether the efficacy of VGX-3100 is able to be enhanced by concomitant treatment with Imiquimod. The Version 3.0 protocol amendment halts enrollment of the VGX-3100 with topical imiquimod study group. All subjects who have already been enrolled into the VGX-3100 with imiquimod study group will continue with all study visits per protocol, but no further participants will be enrolled into this group.

#### **1.1.15 INCLUSION OF WOMAN-PRO, CLINICAL TRIAL VERSION 2.0**

The original WOMAN-PRO (WOMen with vulvAr Neoplasia PRO) was developed by Beate Senn and colleagues [20,31,32] for use following post-surgical intervention. Development of the tool was aligned with the FDA PRO Guidance [33] and included a review of the literature as well as direct patient and expert input. Preliminary measurement properties were assessed in a cross-sectional study. However, despite rigorous development and promising initial measurement properties, gaps in the development and psychometric evaluation exist. To address these gaps, Inovio and collaborators initiated a small qualitative study to confirm the content validity of the tool and support a cross-cultural adaptation of the measure for use in a clinical trial setting of US English and US Spanish speaking subjects. The results of this research is the Clinical Trial of the WOMAN-PRO (2.0) which is utilized in this study.

The WOMAN-PRO Clinical Trial Version 2.0 is a 31 item self-completed patient reported outcome measure designed to assess both physical and psychosocial impacts of VIN. The physical domain is comprised of 15 lesion-related symptoms and includes 5 additional items to measure impact in daily life. Psychosocial constructs are assessment through 11 items that address feelings, thoughts and limitations. Each item is scored using a 4-point Likert scale with higher scores indicating greater difficulty or severity. The recall period is the past week. Details are included in [Section 6.8](#).

#### **1.1.16 POTENTIAL RISKS OF INVESTIGATIONAL PRODUCTS**

Based on the phase 1 and 2 clinical experience, the injection site reactions associated with the IM injection and electroporation are generally mild and limited to a few days in

duration at most. The full risk profile for VGX-3100 is described in the Investigator Brochure.

Local skin and application site reactions are the most frequently reported adverse reactions associated with topical imiquimod 5% treatment. Erythema, erosion, excoriation/flaking, edema, induration, ulceration, scabbing, and vesicles have been reported at the application site [34]. The full risk profile of imiquimod 5% treatment is available in the package insert and prescribing information.

### 1.1.17 POTENTIAL BENEFITS OF STUDY PARTICIPATION

This study has been designed to provide non-surgical treatment with the aim of avoiding the need for surgical excision or laser ablation, which can be disfiguring and have significant associated morbidity. In the absence of complete resolution of vulvar lesions, there would still be potential benefit from a partial response, which would minimize the amount of excisional therapy that may be needed. All currently accepted surgical treatments for VIN are associated with risks inherent with any surgical procedure including anesthesia, post-operative bleeding, infection, or damage to surrounding structures such as the clitoris, urethra, or anus. The other potential benefit is that the response to VGX-3100 is systemic and may clear the underlying HPV infection, which is the root cause of vulvar HSIL. Consequently, there is the potential to reduce the risk of recurrent disease.

## 2. HYPOTHESIS AND STUDY OBJECTIVES

Four 6 mg doses of VGX-3100 (DNA plasmids encoding E6 and E7 proteins of HPV-16 and HPV-18) delivered intramuscularly (IM) followed by electroporation (EP) with CELLECTRA™ 2000 alone or in combination with imiquimod to adult women with histologically confirmed vulvar HSIL associated with HPV-16 and/or HPV-18 (HPV-16/18), will result in a higher percentage of women with regression of HSIL of the vulva based on histology (i.e. biopsies or excisional treatment) and virologic clearance of HPV-16/18 from vulvar tissue compared with historical control.

### 2.1 PRIMARY OBJECTIVE AND ENDPOINT

Objective	Endpoint
Determine the efficacy of four doses of VGX-3100, alone or in combination with imiquimod, with respect to combined histopathologic regression of vulvar HSIL and virologic clearance of HPV-16/18 in vulvar tissue	Proportion of subjects with no histologic evidence of vulvar HSIL  and no evidence of HPV-16/18 at Week 48 in vulvar tissue samples (i.e. collected via biopsy or excisional treatment)  .

## 2.2 SECONDARY OBJECTIVES AND ASSOCIATED ENDPOINTS

Secondary Objectives	Associated Secondary Endpoints
1. Evaluate the safety and tolerability of VGX-3100 delivered IM followed by EP with CELLECTRA™ 2000, alone or in combination with imiquimod	1a. Local and systemic events for 7 days following each dose as noted in the Participant Diary. 1b. All adverse events including SAEs, AESI's, SUSARs, UADEs, and other unexpected AEs for the duration of the study (through Week 100 visit) 
2. Determine the efficacy of four doses of VGX-3100, alone or in combination with imiquimod, as measured by histologic regression of vulvar HSIL	2. Proportion of subjects with no evidence of vulvar HSIL  on histology (i.e. biopsies or excisional treatment) at Week 48 visit
3. Determine the efficacy of four doses of VGX-3100, alone or in combination with imiquimod, as measured by virologic clearance of HPV-16/18 in vulvar tissue	3. Proportion of subjects with no evidence of HPV-16/18  in vulvar tissue samples at Week 48 visit
4. Determine the efficacy of VGX-3100 , alone or in combination with imiquimod, as measured by histologic regression of vulvar HSIL to normal tissue	4. Proportion of subjects with no evidence of vulvar HSIL, no evidence of vulvar LSIL (VIN1), and no evidence of condyloma on histology (i.e. biopsies or excisional treatment) at the Week 48 visit
5. Determine the efficacy of four doses of VGX-3100 , alone or in combination with imiquimod, as measured by non-progression of vulvar HSIL to vulvar cancer as determined by histology	5. Proportion of subjects with no progression  of vulvar HSIL to vulvar cancer from baseline to Week 48 visit
6. Determine the efficacy of VGX-3100, alone or in combination with imiquimod, as measured by reduction in the surface area of the qualifying  vulvar lesion(s)	6. Percent reduction in the cumulative surface area of the acetowhite vulvar lesion(s) as determined by the quantitative analysis of standardized pre-biopsy photographic imaging of the qualifying lesion (s) at Week 48 compared to baseline  . Results will be classified as: no clinically significant lesion resolution (reduction in lesion size of 0-25%), partial lesion area resolution (>25% and <100% reduction), and complete lesion resolution (no visible lesion).
7. Describe the cellular immune response of VGX-3100 administered alone or in combination with imiquimod, post dose 4	7. Flow Cytometry response magnitudes at baseline and Week 27 visits
8. Determine the efficacy of four doses of VGX-3100 alone or in combination with imiquimod with respect to histopathologic regression of vulvar HSIL or viologic clearance of HPV-16/18 in vulvar tissue	8. Proportion of subjects with no histologic evidence of vulvar HSIL  or no evidence of HPV-16/18 at Week 48 in vulvar tissue samples (i.e. collected via biopsy or excisional treatment)

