#### 1.1.3 VULVAR INTRAEPITHELIAL NEOPLASIA (VULVAR HSIL)

HPV-associated vulvar intraepithelial neoplasia (VIN) is a chronic (typically persisting for years), premalignant disorder of the vulvar skin that is caused by persistent infection with one or more high-risk genotypes of HPV. Infected cells produce E6 and E7 oncoproteins constitutively, which increases the degradation of cell cycle regulation proteins p53 and pRb, respectively, resulting in unrestricted cell growth and neoplasia. The basis for progression to cancer is, therefore, attributed to the viral proteins E6 and E7. VGX-3100 specifically induces immune responses against E6 and E7, thereby enabling clearance of pre-malignant cells as demonstrated in the Phase 2 study of cervical HSIL [8].

In 2004, the International Society for the Study of Vulvovaginal Disease (ISSVD) replaced the three grade classification system with the current single grade classification for which only high grade VIN (2/3) is classified as VIN [9]. In 2012, the Lower Anogenital Squamous Terminology (LAST) Standardization Project for HPV-associated lesions applied the term high grade squamous intraepithelial lesion (HSIL) to encompass high grade dysplasia [10]. Therefore, for the purpose of this study, the term vulvar HSIL will be used, which encompasses VIN 2 and VIN 3; the term 'vulvar LSIL' will be used to encompass what was previously known as VIN 1.

Once vulvar HSIL has developed, spontaneous regression is rare, likely occurring in only 1.5% to 5% of women [11]. Over time, typically years, vulvar HSIL can progress to invasive cancer of the vulva, e.g. from treated patients, median: 2.4 years in one group and median 13.8 years in another group [12], and from VIN3 patients, mean = 2.5 years, range: 4 – 216 months [13].

Vulvar HSIL remains a significantly unmet medical condition for the following reasons which will be described further: 1) the rate of recurrence of vulvar HSIL under currently used surgical and medical approaches is extremely high, 2) there is a high psychological and physical negative impact of surgery, 3) vulvar HSIL is symptomatic and impacts activities of daily living, 4) prophylactic HPV vaccines have no therapeutic activity against vulvar HSIL and have not achieved universal uptake, leaving a population of susceptible and impacted women, and 5) the early diagnosis of vulvar HSIL is limited to visual inspection with biopsy.

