## 2.3 EXPLORATORY OBJECTIVES AND ASSOCIATED ENDPOINTS

Exploratory Objectives	Associated Exploratory Endpoints
1. Describe the efficacy of VGX-3100, administered alone or in combination with imiquimod, at Week 74 and/or Week 96 as measured by reduction in the surface area of the qualifying  vulvar lesion(s), in subjects without a complete resolution at Week 48	1. Percent reduction in the cumulative surface area of the acetowhite vulvar lesion(s) as determined by the quantitative analysis of standardized pre-biopsy photographic imaging of the qualifying lesion (s) at Week 74 and/or Week 96 compared to baseline  . Results will be classified as: no clinically significant lesion resolution (reduction in lesion area of 0-25%), partial lesion area resolution (>25% and <100% reduction), and complete lesion resolution (no visible lesion).
2. Describe the long term efficacy of VGX-3100, alone or in combination with prior imiquimod, as measured by histologic regression of vulvar HSIL	2. Proportion of subjects with no evidence of vulvar HSIL on histology (i.e. biopsies or excisional treatment) at Week 74 for subjects who receive 5 doses of VGX-3100 and at Week 96 for subjects who receive 6 doses of VGX-3100.
3. Describe the long term efficacy of VGX-3100, alone or in combination with prior imiquimod, as measured by virologic clearance of HPV-16/18	3. Proportion of subjects with no evidence of HPV-16/18 in vulvar tissue samples at Week 74 and/or Week 96.
4. Evaluate tissue immune responses to VGX-3100, and VGX-3100 with imiquimod, as measured in vulvar tissue samples	4. Assessment of pro-inflammatory and immunosuppressive elements in tissue 
5. Describe virologic clearance of HPV-16/18 from non-vulvar anatomic locations	5. Proportion of subjects who have cleared HPV-16/18 on specimens from non-vulvar anatomic locations without surgical intervention (inclusive of cervix, oropharynx, vagina and intra-anus) at Week 48 compared to baseline
6. Describe association of microRNA (miRNA) profile, previous vulvoscopy, and HPV testing results with Week 48 histologic regression	6. Vulvoscopy, HPV test results (vulvar swab and vulvar tissue) and miRNA profile (Day 0, Week 15 and 48) in conjunction with histologic regression of vulvar HSIL at Week 48 visit

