### 3.2.2 DEFINITION OF RESPONDER AND NON-RESPONDER FOR THE SECONDARY AND EXPLORATORY ENDPOINTS

Table 4: Definition of Responder and Non-responder for HSIL Regression Endpoint	
Responder	Non-Responder
Subject with no histologic evidence of vulvar HSIL AND Subject who did not receive any non-study related treatment for vulvar HSIL	Subject with histologic evidence of vulvar HSIL or vulvar carcinoma at evaluation OR Subject who received non-study related treatment for vulvar HSIL

Table 5: Definition of Responder and Non-responder for Viral Clearance Endpoint	
Responder	Non-Responder
Subject with no evidence of HPV-16 or HPV-18 in vulvar tissue at evaluation AND Subject who did not receive any non-study related treatment for vulvar HSIL	Subject with evidence of HPV-16 or HPV-18 in vulvar tissue at evaluation OR Subject who received non-study related treatment for vulvar HSIL

Table 6: Definition of Responder and Non-responder for Complete HSIL Regression Endpoint	
Responder	Non-Responder
Subject with no histologic evidence of vulvar HSIL, LSIL (VIN1), or condyloma AND Subject who did not receive any non-study related treatment for vulvar HSIL	Subject with histologic evidence of vulvar HSIL, LSIL (VIN1), or condyloma at evaluation OR Subject who received non-study related treatment for vulvar HSIL

Table 7: Definition of Responder and Non-responder for Disease Non-Progression Endpoint	
Responder	Non-Responder
Subject with no histologic evidence of a worsening vulvar condition to vulvar cancer at Week 48 relative to baseline  AND  Subject who did not receive any non-study related treatment for vulvar HSIL	Subject with histologic evidence of worsening of vulvar condition to vulvar cancer at Week 48 relative to baseline  OR  Subject who received non-study related treatment for vulvar HSIL

Table 8: Definition of Responder and Non-responder for HSIL Regression or Viral Clearance Endpoint	
Responder	Non-Responder
Subject with no histologic evidence of vulvar HSIL  OR  Subject with no evidence of HPV-16 or HPV-18 in vulvar tissue at evaluation  AND  Subject who did not receive any non-study related treatment for vulvar HSIL	Subject with histologic evidence of vulvar HSIL or vulvar carcinoma at evaluation  AND  Subject with evidence of HPV-16 or HPV-18 in vulvar tissue at evaluation  OR  Subject who received non-study related treatment for vulvar HSIL

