### 7.1.8 CASUAL RELATIONSHIP OF CLINICAL MATERIAL TO ADVERSE EVENTS

A causally related AE is one judged to have a reasonable possibility of a relationship to the administration of the IP and/or the investigational device. An AE may also be assessed as not related to the IP and/or the investigational device. Because the Investigator is knowledgeable about the subject (e.g., medical history, concomitant medications), administers the IP, and monitors the subject's response to the IP, the Investigator is responsible for reporting adverse events and judging the relationship between the administration of the IP and device and a subsequent AE. The Investigator is aware of the subject's clinical state and thus may be sensitive to distinctions between events due to the underlying disease process versus events that may be product related and may have observed the event. The Sponsor will assess the overall safety of the IP delivered by EP and determine whether to report expeditiously to the regulatory agencies.

Investigators should use their knowledge of the subject, the circumstances surrounding the event, available site and non-site laboratory and clinical records, and an evaluation of any potential alternative causes to determine whether or not an adverse event is considered to be related to the IP and/or the investigational device indicating "yes" or "no" accordingly. Causality should be assessed by the Investigator as "yes, related" or "no, unrelated" by the following criteria:

- Yes – there is a reasonable possibility that administration of the Study Treatment contributed to the event;
- No – there is no reasonable possibility that administration of the Study Treatment contributed to the event and there are more likely causes.

The following guidance should also be taken into consideration:

- Temporal relationship of event to administration of IP and/or the investigational device;
- Course of the event, considering especially the effects of dose reduction, discontinuation of IP, or reintroduction of IP (where applicable);
- Known association of the event with the IP, EP or with similar treatments;
- Known association of the event with the disease under study;
- Presence of risk factors in the Study Subject or use of concomitant medications known to increase the occurrence of the event

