### 7.3.2 STOPPING RULES (CRITERIA FOR PAUSING OF STUDY)

If any of the following situations occur then further enrollment and Study Treatments will be halted until a thorough review has been conducted by the Medical Monitor and PI for the trial, the DSMB, and the IRB/EC (if applicable):

- One third or more subjects experience an AESI verified per protocol definition;
- Any subject experiences an SAE (or potentially life threatening AE), or death verified as related to Study Treatment;
- Three or more subjects experience the same grade 3 or 4 unexpected adverse event, verified per protocol definition and assessed as related to Study Treatment;
- In the event of two identical, unexpected, Grade 4 toxicities, verified per protocol definition and assessed as related to Study Treatment;

Upon conclusion, the sponsor or designee will notify all Investigators and IRBs/EC (if required) regarding the outcome of any investigation stemming from a Study Pause.

Guidelines for assessing relatedness are detailed in [Section 7.1.8](#).

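### The non-progression endpoint stops at Week 48 while PAC-read histology continues to Week 74 or 96, and its definitions disagree on which earlier carcinomas count

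*Protocol*

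**What the plan says.** References are to protocol Version 5.0.

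- Section 1.1.8: "An enhanced monitoring plan will be used in this study to address the risk of a potential delay in treatment of vulvar HSIL".
- Section 2.2, endpoint 5: proportion without progression "of vulvar HSIL to vulvar cancer from baseline to Week 48 visit". Progression means carcinoma on PAC histology.
- Section 3.2.2, Table 7, responder: "Subject with no histologic evidence of a worsening vulvar condition to vulvar cancer at Week 48 relative to baseline", and no non-study treatment for HSIL. Non-responder: "Subject with histologic evidence of worsening of vulvar condition to vulvar cancer at Week 48 relative to baseline", or receipt of such treatment.
- Section 2.3: lesion area, regression, clearance, and regression-or-clearance all have later exploratory endpoints. Regression, for example, is assessed "at Week 74 for subjects who receive 5 doses of VGX-3100 and at Week 96 for subjects who receive 6 doses". None concerns progression.
- Section 3.2: women with HSIL at Week 48 and no lesion growth may receive a fifth dose and are biopsied again at Week 74. Those treated surgically, and Subgroup E, have no further scheduled biopsy.
- Sections 7.1.4, 7.2 and 8.11: histologic progression must be reported as an SAE, SAEs are collected to Week 100 or discharge, and they are tabulated as percentages of subjects.
- Section 7.3.2, one of four pause rules: "Any subject experiences an SAE (or potentially life threatening AE), or death verified as related to Study Treatment".

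**The concern.** Carcinoma is the outcome one would most want to see if waiting for standard treatment does harm, and that delay is what the monitoring plan is there for. The one efficacy measure named after it closes before the period in which women with residual HSIL may receive further study treatment. A report could give complete non-progression while a Week 74 biopsy has shown cancer.

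There is a second problem before Week 48. A woman whose carcinoma is found on an unscheduled biopsy may have no Week 48 tissue, and the definitions do not agree on whether she counts as progression, counts only as treated, or drops out of the analysis.

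**Working it through.** The plan states no progression rate or precision target, so there is no figure of its own to reproduce.

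**1. Histology left out of endpoint 5.** The scheduled biopsies are at Weeks 48, 74 and, for some women, 96.
- To Week 74: (74 − 48)/74 = 26/74 = 35%.
- To Week 96: (96 − 48)/96 = 48/96 = 50%.

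Week 78 is not a suitable end point for this share: it has no scheduled biopsy and may be a phone call.

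**2. Where a Week 74 carcinoma would appear.**

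| Place | Treatment of the case |
|---|---|
| Endpoint 5 and Table 7 | Not counted: both are worded to Week 48 |
| Exploratory endpoints 2 and 9 (Tables 4 and 8) | Pooled with HSIL on the histology component |
| Main safety summary (8.11), which carries exact CIs | Outside: limited to 14 days after a dose; Week 74 is 74 − 52 = 22 weeks after dose 5 |
| Any-time AE and SAE tables (8.11) | Counted, as a reported event term |

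**3. Effect on the stated proportion.** Take the planned 24 women on VGX-3100 alone, all evaluable, none with non-study treatment. The exact (Clopper-Pearson) lower limit with no events is 0.025^(1/n).
- Case not counted: 24/24 = 100%; lower limit 0.025^(1/24) = 85.8%.
- Case counted: 23/24 = 95.8% (78.9 to 99.9%).

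**4. A carcinoma on an unscheduled biopsy at, say, Week 30.**
- Section 2.2 covers baseline to Week 48, so it counts.
- Table 7 asks for histology at Week 48. Section 7.1.4 says she has no further biopsy, so that branch cannot be scored. Whether excising a carcinoma is non-study treatment for HSIL is not stated.
- Section 8.9 opens the efficacy window 14 days before the visit, at Week 46. Week 30 falls outside.
- Section 8.4 restricts the mITT set to women who have the endpoint, and 8.13 imputes nothing, so she may be dropped.
- The explicit rule that any confirmed progression is non-response stands in 3.2.1, for the primary endpoint only.

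If she is dropped, the result is 23/23 = 100% with lower limit 0.025^(1/23) = 85.2%. If she is counted, it is 23/24 = 95.8%.

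**5. Upper end of the window.** Section 8.9 gives a start but no end. Read literally, it could admit tissue taken well after the Week 48 visit, which conflicts with 2.2 and Table 7.

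**6. How many cases might be involved (assumed rates only).** With a constant annual hazard a, p = 1 − exp(−a × weeks × 7/365.25). For 36 women, all followed:

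| Assumed annual hazard | Expected by Week 48 | By Week 74 | By Week 96 |
|---|---|---|---|
| 1% | 0.33 | 0.51 | 0.66 |
| 2% | 0.66 | 1.01 | 1.30 |
| 5% | 1.62 | 2.46 | 3.16 |

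At 2% the chance of at least one case is 48% by Week 48 and 64% by Week 74. The later columns are too high for this trial, because surgically treated women and Subgroup E have no further scheduled biopsy and few women reach Week 96.

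**7. Pause rules.** Each needs relatedness; for adverse events of special interest it is part of the definition in 7.3.1. Section 7.1.8 calls an event related when "there is a reasonable possibility that administration of the Study Treatment contributed to the event". A carcinoma judged related pauses the trial on its own. One attributed to the underlying disease meets no rule.

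**The case against.** The Week 48 horizon has a reason. Objective 5 concerns four doses, and Week 48 is the last scheduled histology before a fifth dose or surgery. Later results mix women treated differently. This stands, and it is why the Week 48 proportion should be kept.

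Three stronger readings are tempting, and the documents support none of them.

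- *That no cancer rate exists after Week 48.* Carcinoma is a mandatory SAE, collected to discharge and tabulated as a percentage of dosed women whenever it occurs. What is missing is a PAC-based proportion with an interval.
- *That carcinoma cannot trigger a pause.* One case verified as related does. Relatedness is judged case by case, and an unrelated verdict requires that contribution be not reasonably possible. The Data Safety & Monitoring Board (DSMB) also sees safety and regression data quarterly, may meet ad hoc, and may recommend suspension without any relatedness condition (10.4.1). Its charter is not shown.
- *That the protocol's own time to cancer puts more of the risk after Week 48.* The figure in 1.1.3, "mean = 2.5 years, range: 4 – 216 months", gives no hazard and says nothing on how risk is spread within this study.

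Table 7 also counts non-study HSIL treatment as non-response, so even the Week 48 figure is not a pure progression rate.

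**Conclusion.** The point holds as one of endpoint definition. The PAC-based non-progression proportion omits 35% of the scheduled histology period to Week 74, or 50% to Week 96, and the three passages that define it do not agree on carcinomas found off schedule before Week 48. One uncounted case among 24 women is the difference between 100% and 95.8%. With so few women the interval is wide either way, so what matters is whether a case is visible in the endpoint, more than precision.

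This does not show that cancers go unreported or that safety oversight lacks a route to act. The size in step 3 assumes 24 evaluable women with no non-study treatment. The expected counts in step 6 rest wholly on assumed rates. It is worth correcting because the specimens and readings are already planned.

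**What to change.** In endpoint 5 and Table 7, define progression as any PAC-confirmed carcinoma from first dose, including those from unscheduled biopsies and excisions, counted in all dosed women whether or not Week 48 tissue exists. Keep the Week 48 proportion for the four-dose objective. Add the same proportion through the last on-study histology, by arm, with exact CIs. Show carcinoma separately from the non-study-treatment component of Table 7. Since women without tissue would count as having no confirmed carcinoma, state how many had histology at each horizon. Align the window in 8.9 with these definitions.

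Add no pause rule to 7.3.2: anything listed there halts enrolment and treatment. At most, 10.4.1 or the DSMB charter could state that each PAC-confirmed carcinoma is notified to the existing DSMB whatever its relatedness, leaving every treatment decision to the DSMB and investigators.

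The cost is wording and one more table row, with no new procedure. The drawback for the sponsor is that the non-progression figure may be less favourable.
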